All key personnel have been HIPAA trained. All data will be encrypted and stored on secure servers within the hospital data center, with access restricted based on involvement in the project. Patients will also be offered multiple methods of withdrawing participation consent from the study, which includes by phone, email, website, and nursing care.

9. Subjects - Participation

Duration of an Individual Subjects Participation in the Study

During the entirety of their care on 9W, 9E, 10W, 10E

Duration Anticipated to Enroll All Study Subjects

We anticipate, given the current volume of bed movements, that it will take 30 months to complete enrollment.

Estimated Date for the Investigators Within 3-5 years
to Complete This Study

Procedures for Subjects to Request Withdrawal

Subjects may also withdraw from permission for the use and disclosure of any of your protected information for research and can do so by contacting the unit business associate "BA", by email to [contact] or by calling to [contact] with the information specified in "Waiver Information Sheet" (Appendix 1).

Procedures for Investigator to Withdraw Subjects

The Principal Investigator may stop subject involvement in this research study at any time without subject consent. This may be because the research study is being stopped, the instructions of the study team have not been followed, the investigator believes it is in their best interest, or for any other reason.

"Not participate" or "withdraw" means the alerting will be suppressed/turned off for the patient, their data will not be collected, and no alerts will be sent. Any data or alerts prior to withdrawal will be retained. This information has been added to the consent.

Participants Will Be Recruited Yes

Recruitment Method(s) Clinical Practice

How Participants Will Be Identified

All patients admitted to 10E, 10W, 9E, and 9W

Who Will Initially Approach Potential Participants Clinic Personnel

How Research Will Be Introduced to Participants

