Description of the study protocol will be given to participants upon admission to the floor. We will instruct the Business Associate and nursing team members to specifically call to attention to the provided information sheet when a patient is admitted to the unit. We will also post prominent printed notices describing the study throughout the unit (e.g. on the walls near the nursing desk, on any bulletin boards designed for patient communication, etc). Furthermore, if a patient does trigger an alert, the RRT staff will be instructed to notify the patient of the information sheet. Finally, upon discharge, the information sheet would be provided again to the patient as part of their check-out. As such, there exists at least 3 touch points for the patient to discuss the study with a care provider.

How Participants Will Be Screened

Automated screening by the software that generates alerts.

10. Subjects - Risk and Benefits

Risks to Subjects

The MEWS++ alerts will serve to notify the care team of a potential deterioration in a patient's clinical condition. What the provider may choose to do with the MEWS++ alert is left completely to their discretion and we do not propose any determination of care by the MEWS++ alert. As a result, there will be no alteration in the standard of care. All therapeutic interventions will be at the discretion of the care providers and the expected risk of monitoring for select individuals within the interventional cohort should be minimal. The potential risk of breach of confidentiality or loss of protected healthcare information (PHI), will be unlikely as all data will be password protected and any patient identifiers will be encrypted; furthermore, all data gathering will be done on Mount Sinai internal network computers and devices.#

We do not change any workflow for the primary team and RRT. We just increase awareness in the clinicians' mind that a patient may be in danger of deterioration. The primary intervention by the Primary team is simply to increase the frequency of vitalsigns measurement. This will not be associated with any risk or patient safety concerns. We will not remove any of current notifications being received by RRT we will just add one more notification to the current workflow.

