Description of the Source Records that Will Be Used to Collect Data About Subjects

For each patient, real-time data from the EHR, the admitting system (Cerner ADT), the ECG (MUSE), and laboratory information systems (SCC) will be ingested by the ReSCUE-ME engine and used to generate a prediction score. Additional information provided by the RRT team on the result of the RRT intervention will be extracted from REDCap. These values as specified in Appendix 3 will be processed through the ReSCUE-ME data streaming engine to generate a MEWS++ score for patients who have not been excluded or withdrawn from the study. If an individual withdraws participation from the study, all data pertaining to this patient's current visit will be removed from

ReSCUE-ME. Clinical documents may also be assessed for the purpose of further clarification of events during the RRT intervention.

Description of Data that Will Be Collected Including Long-Term Follow-Up

The data that will be collected during this study include vitals, electrocardiogram, laboratory data, clinical evaluations, and patient demographics from ADT, Epic, MUSE, and Laboratory Information System. A detailed list is provided in Appendix 3. At this time we do not plan on conducting long-term follow-up upon the discharge of the patient from their current hospital visit.

Research Requires HIV Testing No

12. Procedures - Genetic Testing

Genetic Testing Will Be Performed No

Guidance and Policies > Future Use Data Sharing and Genetic Research

13. Procedures - Details**Surveys or Interviews** Yes**Type of Instruments Being Used** Created By Research Team**Description of Instruments Created By Research Team**

A REDCap survey will be created to understand the impact of the alerts on the RRT team. This clinician survey has not yet been developed. We will not do this piece of the research until the survey has been approved by the IRB and the protocol modified appropriately and also approved.

Audio / Photo / Video Recording No**Deception** No**Results of the Study Will Be Shared** No
with Subjects or Others

14. Procedures - Instruments**Instruments Created By Research Team**

Type	REDCap RRT survey
Name	REDCap RRT survey
Upload	REDCap RRT Survey Placeholder.docx

15. Procedures - Compensation

Compensation for Participation No

16. Consent - Waiver of Informed Consent

Requesting Waiver For

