At the request of the IRB, the principal investigator developed the following opt out process in cases where patients did not want to participate:

Opt-Out Process for ReSCUE-ME

1. Every patient will receive at least one printed copy of the "Waiver Information Sheet" letter at various entry points into the hospital unit:
 - a. The 9W, 9E, 10W, and 10E business associate will insert a print out of this waiver into their "welcome packet" (a packet of information given to all patients entering any hospital unit) as part of the current standard operating procedure.
2. We will offer to distribute this letter to every hospitalist through Mount Sinai Medicine Department's Division of Hospital Medicine.
4. The opt-out letter will be in English and Spanish.

Educating Nursing and Physicians about the Opt-Out Process

1. An educational conference will be partially devoted to the subject of introducing the study and explaining the scientific background and methods of the research.
 - a. Medicine Department's Division of Hospital Medicine
 - b. The Mount Sinai's Institute for Critical Care Medicine
 - c. Nursing Teams on the participating units.
2. All members of the hospitalist and rapid response care team (attending, residents, and nursing) will be given a script that will be posted on the departmental intranet to give patients information regarding the study.
3. All members of the hospitalist care team and business associates on the participating units will be given instruction as to the procedure for withdrawing patients from the study.

Instructions for Hospitalist Care Team:

1. If the patient has no questions regarding the ReSCUE-ME Study, then proceed as usual.
2. If the patient has questions regarding the ReSCUE-ME Study that you cannot answer, please page one of the investigators listed on the Clinical Data Science group's intranet link for the study. If you cannot obtain an answer quickly for the patient, offer the patient the option of withdrawing from the research.
3. If the patient spontaneously, or after having had questions answered, wishes to withdraw from the research, the provider should submit a request to the <http://cds.mountsinai.org/ReSCUEMe> website.

Type of Waiver

Waiver of Consent

How the Research Involves No More Than Minimal Risks to Participants

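### The protocol has two conflicting rules for a withdrawn patient's earlier data and the final SAP does not choose; if visits were deleted, alert-linked opt-out could bias one arm

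*Combined protocol and SAP*

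**What the plan says.** Section 9 (Subjects - Participation), in the text on withdrawing subjects, defines withdrawal for the future: "the alerting will be suppressed/turned off for the patient, their data will not be collected, and no alerts will be sent". For the past it says: "Any data or alerts prior to withdrawal will be retained". It adds that this was put into the consent.

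Section 11 (Procedures - Narrative), in the description of source records, says: "If an individual withdraws participation from the study, all data pertaining to this patient's current visit will be removed from" ReSCUE-ME.

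Section 9 also lists when patients are told about the study. All get the sheet on admission. Then, "if a patient does trigger an alert, the RRT staff will be instructed to notify the patient of the information sheet". Last, "upon discharge, the information sheet would be provided again to the patient as part of their check-out". This sheet carries the withdrawal instructions, and the opt-out process in Section 16 calls it a letter for that purpose: "The opt-out letter will be in English and Spanish". Sections 7 and 11 say that 9W and 9E receive no alerts.

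The final SAP (December 2021) analyses the first hospitalization by study arm at admission, with inverse probability weights built on baseline characteristics. It has no rule for withdrawn patients and no count of them. The document states that the final protocol was the same as the original, so both withdrawal sentences stood throughout.

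**The concern.** For a patient who opts out mid-stay, the two sentences cannot both govern the same dataset. One keeps the stay up to withdrawal; the other removes it.

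The choice matters because one reminder about opting out depends on arm and risk. The pointer that follows an alert can occur only on 10E and 10W, and only after the model has flagged likely deterioration. If opting out then deletes the visit, membership of the analysis set depends on an event after assignment that is linked to the outcome, in one arm only. Weights built on baseline characteristics do not correct that. The direction is predictable: the observed escalation rate in the intervention arm would fall.

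**Working it through.** The plan states no figure on this point, so there is none to reproduce. The text comparison comes first, then an illustration of size.

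**Text.**
- Past data: Section 9 keeps it; Section 11 removes all of the current visit from ReSCUE-ME.
- Future data: collection stops at withdrawal under either rule.
- Meaning of the name: the same part of Section 11 speaks of a ReSCUE-ME engine and a data streaming engine, but ReSCUE-ME is also the protocol title. The text does not say which is meant.
- Alert-linked reminder: intervention units only. The SAP's summary of changes says alerts were capped in both arms. Under the protocol none were to be acted on in control, so this does not create a matching reminder there.

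**Illustration, assuming deletion and no true effect.** Inputs:
- p = 0.10, escalation rate (Section 19, sample size calculation)
- s = 0.76 and c = 0.68, pilot sensitivity and specificity (Section 3)
- 9340 bed movements per arm (Section 19)
- w = excess share of alerted patients who opt out. The documents give no value, so a range is assumed.

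Alerted share: a = p·s + (1 − p)(1 − c) = 0.076 + 0.288 = 0.364.

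Escalation among alerted: 0.076 / 0.364 = 20.9%. Among the rest: 0.024 / 0.636 = 3.8%.

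Observed intervention rate after deletion: (p − p·s·w) / (1 − a·w). For w = 10%: (0.100 − 0.0076) / (1 − 0.0364) = 9.59%.

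| w | Visits deleted of 9340 | Observed rate | Shift (points) | Two-sided 5% test: false-positive rate |
|---|---|---|---|---|
| 1% | 34 | 9.96% | 0.04 | 5.1% |
| 5% | 170 | 9.80% | 0.20 | 7.45% |
| 10% | 340 | 9.59% | 0.41 | 15.5% |
| 20% | 680 | 9.15% | 0.85 | 49.5% |

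The last column uses a simple comparison of two proportions with independent bed movements, not the SAP's weighted models.

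Benchmark: Section 19 expects at least 50% of escalations to be identified and about 20% of those prevented, so 10% × 50% × 20% = 1 point.

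**Two checks on the inputs.**
- The pilot reports a precision of 0.3, not 20.9%. Holding p = 0.10, s = 0.76 and precision at 0.3 gives a = 0.076 / 0.3 = 0.253, and shifts of 0.05, 0.26, 0.52 and 1.07 points. The picture is similar.
- The share of 36.4% is an upper figure for those prompted. The reminder runs through RRT staff, who are notified directly only above a score of 0.64, and Section 3 does not say which threshold the pilot figures describe. A given w among all alerted patients therefore needs a higher opt-out rate among those whom RRT staff actually see.

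**Retention does not settle it alone.** Take the extreme case where every escalation of a withdrawn alerted patient follows withdrawal, is not collected, and the patient is coded as not escalated. At w = 10% the rate is 0.100 − 0.0076 = 9.24%, a larger shift than deletion gives. The coding rule for binary outcomes has to be stated.

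**The case against.** Several objections have force, and three stronger readings should be set aside.

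*A reader might infer that opted-out visits were erased from the trial data.* The documents do not show this. Removing a patient from a live scoring engine while keeping earlier research data is a plausible reading of Section 11, and it would dissolve the conflict. RRT results are held in REDCap, and other sources are the chart and data warehouse. Section 9 defines withdrawal explicitly and says the definition went into the consent, which favours retention. The opt-out handling procedure and program specification (Appendices 2a and 2b) may settle it, but their content is not in the text reviewed. What stands is that the protocol wording is ambiguous and the SAP is silent.

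*A reader might infer that each alert triggers an offer to withdraw.* Section 9 describes a reminder of the sheet. Section 16 tells the hospitalist team to proceed as usual if there are no questions, and to offer withdrawal when questions cannot be answered quickly.

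*A reader might infer that the discharge sheet adds to the bias, because patients who died never receive it.* It is described without distinguishing units, so it is not by itself a difference between arms.

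Finally, nothing in the documents supports opt-out rates of 10% to 20%. At 1% the shift is 0.04 points.

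**Conclusion.** The conflict is real and unresolved: two sections of one application state different rules for data from before withdrawal, and the final SAP names neither. The risk of bias is conditional. It requires that Section 11 meant deletion from the analysis data, that the reminder after an alert led to extra opt-outs, and that these were not rare. Under those conditions the bias favours the intervention. It is negligible at about 1% excess opt-out, becomes material at roughly 5% to 10%, and approaches the planned 1-point effect at 20%. These sizes rest on the pilot sensitivity and specificity, a 10% escalation rate and an assumed opt-out range; the actual rate is not given. This is a point to put right and report on, not evidence that the result is biased.

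**What to change.** 1. Adopt the Section 9 retention rule for both arms, after checking it against the two information sheets (Appendices 1a and 1b). Reword the Section 11 sentence so that removal applies at most to the live scoring engine.
2. State in the SAP that withdrawn patients stay in their initial arm with data up to withdrawal. Use time at risk as an offset in the negative binomial models, censor length of stay at withdrawal in the Cox model, and give an explicit rule for the logistic outcomes, which cannot take censoring.
3. Report withdrawals by arm, alert status and timing (before any alert, after an alert, at discharge).
4. Collection stops at withdrawal under either rule, and stopping after an alert is informative. If the counts are not trivial, add a bounding analysis that sets the unobserved outcomes to each extreme by arm.
5. If visits were in fact deleted, report the number per arm.

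Cost: one protocol sentence, a short SAP paragraph, one table and a few partly observed stays. Requests were to go through a website, so counts should be obtainable, although the text does not confirm that a log exists. If they are very small, the table closes the matter.

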Receipt or Transmission of Data	No
Holding Code That Can Be Linked to Identity of Participants	No

Duration Data Will Be Stored

Data are stored in accordance with the data retention policy of the manuscript in which the results will be published. This may vary by publication but is generally 7 years.

Steps That Will Be Taken to Secure the Data During Storage, Use, and Transmission

Only the designated investigator and co-investigators as listed on this form will have access to patient data used in this study and will be the sole arbiters for receipt and transmission of this data. The data will be password protected on Mount Sinai computers. Data are encrypted both at rest (i.e., when stored in the database) and while in motion (i.e., during transit between various components of the alerting system) using industry standard encryption protocols. Data will only be accessed from within the Mount Sinai network to ensure confidentiality, which is also password protected and physical access restricted. Any presentation will separate the presented material from the associated identifiers. All individuals have completed institutionally approved HIPAA training.

Power Analysis/Data Analysis Plan (Including Any Statistical Procedures)

Sample size calculation

Based on the pilot feasibility study, the current true rate of escalation of care in the selected units is ~ 10%. We expect that MEWS++ will identify at least 50% of the escalations, on average ~ 6 hrs before the expected time of deterioration/escalation. It is estimated that RRT and front-line providers collaboratively will be able to prevent ~ 20% of the predicted escalations. We are specifying a non-inferiority or superiority margin of 5%. As a result, the estimated sample size needing to achieve a type 1 error of 5% and power of 95% is 934. based on the rate of escalation ~ 10%, a total of approximately 9340-bed movements will need to be recruited for this study in the MEWS++ group and a total of 18680-bed movements across both groups. We assumed that there is not a significant

difference in the escalation rate between the selected units (10E and 10W) and control units (9E and 9W). Interim evaluations every 6 month will be conducted and if at any point the model meets statistical significance or major flaws identified, a subsequent report will be submitted.

Statistical Analysis:

#The basics of generating a MEWS++ score, the sources of the data and where the results will be made available to the floor patient care providers is described under "Procedures > Narrative" section of this IRB. Briefly, a random forest model has been trained to generate a prediction score based on 36 clinical variables. This score represents the likelihood of clinical deterioration. For all interim reports, final study outcome report, and publication analysis our research team plans to use an array of parametric and non-parametric statistical approaches to evaluate the significances of the primary and secondary endpoints. These would include, but not limited to binomial proportion tests, students t-tests, Mann-Whitney U test, Fisher's exact test, and ANOVA. Additionally, we plan to examine any potential significant difference in the demographics of the patients admitted to 10W and 10E when compared to 9W and 9E, significant differences will be incorporated into a multi-varient model such as a linear/logistic regression model to further elucidate factors that may have confounded the # of RRT evaluation and escalation events.

20. Data - Safety Monitoring

More Than the Minimum Data Safety Monitoring Will Be Done No

The following minimum requirements apply to all projects, including retrospective reviews of medical records, use of tissue samples, and many minimal risk studies, such as observational and survey research. Because these minimum requirements apply to all studies, a specific written DSMP will not usually be required for projects that do not pose greater than minimal risk to subjects. The MSSM PPHS may alter the required level of monitoring if appropriate.

For all projects, the principal investigator must have a plan to assure that data integrity will be maintained during its collection, storage and analysis. All research projects must adhere to MSSM recommendations on the storage of research data. Loss of data containing identifiable information is reportable to the IRB within 5 business days.

Any problems concerning the consent process and any subject complaints should be monitored by the investigator. Reports of such problems must be made at least annually. The discretion of the protocol director will guide the need to report these problems immediately or more frequently.

The principal investigator is, typically, the monitoring entity for the minimum DSMP. When a principal investigator is not a faculty member, the supervising faculty member must be responsible for the data and safety monitoring aspect of the protocol.

Will the Research Include Data Coordinating Center Activities? No

21. Financial Administration

This information will help the Financial Administration of Clinical Trials Services (FACTS) office determine whether a Medicare Coverage Analysis (MCA) is needed for the research study. If you have any questions while completing this form, please contact the FACTS office at [contact] or [contact].

Clinical Research Study Category Investigator Initiated

Payment Options:

- * Option 1: No protocol-required services will be billed to patients or third-party payers. Does Not Need MCA***
- * Option 2: Protocol-required services (i.e., routine care services) will be billed to patients or third-party payers. Must Have MCA***
- * Option 3: Study is initiated and federally funded by a Government Sponsored Cooperative Group who will only pay for services that are solely conducted for research purposes and other protocol-required services (i.e., routine care services) will be billed to patients or third-party payers. Billing Grid Only Required, NO MCA***
- * Option 4: Study involves only data collection and has no protocol-required clinical services. Does Not Need MCA***
- * Option 5: Study is not described in any of the above options. Please describe the study and specify whether External Sponsor (i.e., industry, government, or philanthropic source) and/or patient/third party payer will pay for protocol required services. MCA MAY Be Required***

Payment Option Option 4

No MCA is needed per option selected above.

22. Attachments

Type	Name	Version	Status	Filename	Uploaded Date
Data Collection Sheet	Appendix 3 - DataElements.xlsx	1	New	DataElements.xlsx	03/04/2019
Other - Other IRB Correspondance	Appendix 2a - RESCUE ME Opt-out Request Handling Procedure.docx	1	New	Appendix 2a - RESCUE ME Opt-out Request Handling Procedure.pdf	03/05/2019
Other - Other IRB Correspondance	Appendix 2b - Specification for Opt-out Computer Program.docx	1	New	Appendix 2b - Specification for Opt-out Computer Program.docx	06/11/2019
Other - Other IRB Correspondance	Appendix 4a - Notification Process Primary.pdf	1	New	Appendix 4a - Notification Process Primary.pdf	03/05/2019
Other - Other IRB Correspondance	Appendix 4b - Notification Process RRT.pdf	1	New	Appendix 4b - Notification Process RRT.pdf	03/05/2019
Other - Other IRB Correspondance	Appendix 5 - HRP416 Waiver of Consent Documentation	1	New	Appendix 5 - HRP416 Waiver of Consent Documentation.pdf	04/25/2019
Other - Participant Educational Materials	Appendix 1a - Waiver-Consent Information Sheet- CASES.docx	1	New	Appendix 1a - Waiver-Consent Information Sheet- CASES.docx	06/11/2019
	Appendix 1b - Waiver-Consent Information Sheet- CONTROLS.docx	1	New	Appendix 1b - Waiver-Consent Information Sheet- CONTROLS.docx	06/11/2019
Instruments	REDCap RRT Survey Placeholder.docx	1	New	REDCap RRT Survey Placeholder.docx	06/11/2019

Final Protocol

The final protocol was the same as the original protocol. No changes were made to the protocol during the study period.

Original Statistical Analysis Plan As submitted to the IRB Mar-June 2019

For all interim reports, final study outcome report, and publication analysis our research team plans to use an array of parametric and non-parametric statistical approaches to evaluate the significances of the primary and secondary endpoints. These would include, but not limited to binomial proportion tests, students t-tests, Mann-Whitney U test, Fisher's exact test, and ANOVA. Additionally, we plan to examine any potential significant difference in the demographics of the patients admitted to 10W and 10E when compared to 9W and 9E, significant differences will be incorporated into a multi-variant model such as a linear/logistic regression model to further elucidate factors that may have confounded the # of RRT evaluation and escalation events.

Final Statistical Analysis Plan

December 2021

Data from the first hospitalization for each patient during the study period were included in the study. The analyses focused on patient level, unit level, and alert level, individually. All variables were summarized using the appropriate descriptive statistics. Continuous variables were presented as mean (standard deviation) or median [interquartile range], as appropriate. Two-sample t test was used to examine differences in means and Kruskal-Wallis test was used to assess differences in median between study arms. Categorical variables were presented as count (percentage). Chi-square test was used for categorical variables associated different study arms.

Patient Level Analysis

Study arm at admission was used to define the treatment group throughout the patient level analysis. The intervention group referred to the patients initially assigned to the MEWS intervention, and the control group referred to the patients initially assigned to the non-MEWS intervention. Propensity score modeling with inverse probability of treatment weight (IPTW) was used to account for differences in baseline characteristics for patients between two treatment groups. To reduce influence from extreme weights, we used stabilized weights, where the weight for a MEWS subject was the proportion of subjects receiving MEWS divided by the subject's propensity score, and the weights for a non-MEWS subject was the proportion of subjects receiving non-MEWS divided by one minus of the respective propensity score. These weights were then incorporated into all subsequent analyses.

IPTW Negative binomial regression models were used to model the count data during the entire hospital stay, including the total number of RRT alerts, escalations, blood pressure support, medical orders, laboratory orders, and all orders. Treatment effect is expressed in terms of the adjusted ratio of the two counts between the intervention group and the control group. IPTW Logistic regression models were used to model the binary outcomes, including death within 30 days after admission, death in hospital, ever being escalated, and whether any medical or laboratory orders were ordered. Treatment effect is expressed in terms of the adjusted odds ratio. IPTW Cox proportional hazard regression analysis was used to assess the association of study arm with hospital length of stay. The hazard ratio is used to describe the relative probability of hospital discharge at a given time. A hazard ratio >1 is associated with a shorter hospital stay. As a confirmatory analysis, we also performed the regular covariates-adjusted regression analysis using the same set of predictors used in the propensity score model.

Alert and Unit Level Analysis

At the alert level, the status of ICU escalation, whether a type of medical order or laboratory order is placed, and the total number of medical orders and laboratory orders following each alert were summarized. The descriptive summary of alert level analysis was also performed for the subset of RRT alerts and primary alerts. Confusion matrices were used to analyze the performance of RRT alert versus none alert and any alert (rrt alert or primary alert) versus none alert, individually, in association with actual escalation and actual escalation to ICU within MEWS arm where all patients received MEWS escalation monitoring and provider alerting. In the floor unit level analysis, escalation status, ICU status, alert levels, and the total number alerts were summarized.

Statistical Analysis Plan Summary of Changes

Primary outcome

Analysis was limited to first hospitalization. For patients who had crossover between intervention and control arms, treatment group was determined by initial study arm from the first unit admission. Inverse probability of treatment weight was chosen as the method to account for differences between treatment arms.

Secondary outcomes

The analysis of the secondary outcomes was modified as follows:

Secondary Outcome Number	Secondary Outcome Description	Modification
3	Number of participants requiring respiratory support	This outcome was removed due to too few events. Only 20 respiratory therapy orders were placed across both intervention and control groups.
4	Number of cardiac arrest episodes	This outcome was removed due to too few events. There were no episodes of cardiac arrest.
5	Mortality Rate	This was further clarified to be combined in-hospital and 30-day mortality.
6	Notification Frequency	This outcome was removed. As implemented, the number of alerts generated per patient was capped at 3 per unit admission in both arms.
7	Number of calls	This outcome was removed. It was intended to measure the number of calls to RRT initiated by clinicians independent of the alert system. Low data quality in the separate RRT call tracking system made the data unusable.

Ad-hoc outcomes

The following ad-hoc outcomes were added:

1. Likelihood of ICU escalation within 12 and 24 hours
2. Likelihood of earlier hospital discharge
